## 13.8 Analysis of Secondary Endpoints

The **safety analysis** will be performed in all subjects receiving combination olaparib and IV ascorbic acid. AE data will be listed individually and incidence of AEs summarized by system organ class and preferred terms within a system organ class for each treatment group. When calculating the incidence of AEs, each AE (based on preferred terminology defined by Medical Dictionary for Regulatory Activities (MedDRA; Version 13.1, or later) will be counted only once for a given subject. In analyses of grade and causality, if the same AE occurs on multiple occasions, the highest grade and strongest relationship to study drug will be assumed. If 2 or more AEs are reported as a unit, the individual terms will be reported as separate experiences. Changes in vital signs, hematology and clinical chemistry parameters from baseline to the end of the study will be examined. Toxicity will be tabulated by type and grade. Toxicities will be characterized according to the CTCAE version 5.0 Treatment-emergent changes from normal to abnormal values in key laboratory parameters will be identified.

Radiographic progression-free survival (**rPFS**) is defined as the number of months from initiation of therapy (cycle 1, day 1) to date of first radiographic progression, death from any cause, or last patient evaluation. Patients must receive at least one dose of olaparib and IV ascorbic acid to be considered evaluable. Radiographic progression will be determined by modified RECIST criteria 1.1 by development of two or more new bone lesions not consistent with tumor flair for prostate cancer working group 2. Patients who have not progressed or died will be censored at the last date they were assessed and deemed progression-free. rPFS will be summarized and six month estimates for rPFS will be reported using the Kaplan-Meier method with 90% confidence intervals.

**PSA doubling time** from baseline is a time-to-event outcome. Time in months is measured from the initiation of therapy (cycle 1, day 1) until the PSA has increased to 200% of baseline value after a minimum of 12 weeks of therapy and has been confirmed with another measurement at least 4 weeks later, or death. The date of PSA doubling will be the first value recorded (not the confirmatory value). Patients must receive at least one dose of olaparib and IV ascorbic acid to be considered evaluable. PSA doubling time will be summarized using the Kaplan-Meier method with 90% confidence intervals.

Prostate-specific antigen progression-free survival (**PSA PFS**) is defined as the number of months from initiation of therapy (cycle 1, day 1) to first PSA failure (two consecutive increases in PSA of 50% at least 4 weeks apart and ≥5 ng/mL above nadir) or death. Patients must receive at least one dose of olaparib and IV ascorbic acid to be considered evaluable. Patients who do not experience PSA failure or die will be censored at the last date of PSA measurement. PSA PFS will be summarized using the Kaplan-Meier method with 90% confidence intervals.

**OS** is defined as the number of months from the initiation of therapy to death due to any cause. Patients who are alive or lost to follow up as of the data analysis cutoff date will be

censored at the last date they were assessed. OS will be summarized using the Kaplan Meier method with 90% confidence intervals.

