#### 3.0 STUDY DESIGN

This is a multi-center phase II study to evaluate the safety and clinical activity of the combination of olaparib and high-dose IV ascorbate, as second or later line of therapy, in castration resistant prostate cancer patients with no known DNA repair gene mutations (DDRm). In brief, the primary endpoint is  $PSA_{50}$  response, defined by a 50% reduction in PSA from baseline. The secondary endpoints are assessing the PSA doubling time, radiographic and PSA PFS, safety and tolerability as defined by the incidence of grade 3 to 5 toxicities, and measuring overall survival. For complete endpoint definitions, see **Sections 13.2-13.4**. The total accrual for this clinical trial will be 12 men with castration resistant prostate cancer (n=12).

Olaparib will be administered at 300 mg PO BID; ascorbate will be administered at 1 g/kg IV twice weekly at least 24 hours apart until objective disease progression or unacceptable toxicities or patient withdrawal for other reasons.

The study will consist of a screening period (within 28 days of the first dose), treatment period, and follow-up period. Dose reductions are allowed per **Section 8.2.** Enrollment will continue until 15 subjects (allows for 3 drop outs) have received at least one dose of study treatment.

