# 9.3.3 Attributing Causality

The relationship of an AE to the administration of the study drug is to be assessed by the investigator according to the following definitions:

- No (unrelated, not related, no relation): The time course between the administration of study drug and the occurrence or worsening of the adverse event rules out a causal relationship and another cause (concomitant drugs, therapies, complications, etc.) is suspected.
- Yes (related): The time course between the administration of study drug and the occurrence or worsening of the adverse event is consistent with a causal relationship and no other cause (concomitant drugs, therapies, complications, etc.) can be identified.

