# 13.3 Secondary Endpoint Definitions

- Safety and tolerability will be defined by frequency of the drug-related adverse events by grade as assessed by the NCI CTCAE Version 5.0, lab measurements, and vital signs.
- Radiographic progression will be defined as soft tissue disease progression by modified RECIST criteria 1.1 (baseline LN size must be >1.0 cm to be considered target or evaluable lesion) or by development of two or more new bone lesions not consistent with tumor flair for prostate cancer working group 3. Radiographic progression free survival (rPFS) is defined as the number of months from initiation of therapy to date of first radiographic progression, death from any cause, or last patient evaluation. Patients who have not progressed or died will be censored at the last date they were assessed and deemed progression-free.
- Time to PSA doubling from baseline is a time-to-event outcome. Time is measured from the initiation of therapy until the PSA has increased to 200% of baseline value, and confirmed with another measurement at least 4 weeks later, or death. The date of PSA doubling will be the first value recorded (not the confirmatory value).
- PSA PFS is defined as time to first PSA failure (two consecutive increases in PSA of 50% and ≥5 ng/mL above nadir) or death.
- OS is defined as the number of months from initiation of therapy to death due to any cause.

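### The Section 13.8 rule for repeated adverse events does not tie grade and relationship to one episode, so the drug-related rate by grade can be overstated

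*Combined protocol and SAP*

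**What the plan says.** Section 13.3 sets the endpoint: "Safety and tolerability will be defined by frequency of the drug-related adverse events by grade". An event enters that frequency only if it is drug-related, and it enters at its own grade, so the endpoint is a joint classification.

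Section 13.8 says how repeats are reduced. Each term "will be counted only once for a given subject". Where a term recurs, the rule reads: "if the same AE occurs on multiple occasions, the highest grade and strongest relationship to study drug will be assumed". The scope given for it is "In analyses of grade and causality". This is the plan's only rule for repeats. It does not say that grade and relationship must belong to the same episode. It also does not say whether it serves one table of relationship by grade or two separate summaries.

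Two other passages leave relationship out. Section 13.8 adds: "Toxicity will be tabulated by type and grade". Section 3.0 describes the endpoint as "safety and tolerability as defined by the incidence of grade 3 to 5 toxicities".

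Relationship is recorded as yes or no for each event under Section 9.3.3. Section 13.8 also provides for an individual listing of adverse events.

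**The concern.** A maximum taken over grade and another taken over relationship can come from different episodes. Each is correct in a table of its own. Put together in one cell, they can describe an event that the investigator never assessed.

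Safety and tolerability is the first secondary objective, and Section 4.2.8 states that there are no clinical data on this combination in castration-resistant prostate cancer. With 12 to 15 patients, one reclassified patient visibly moves a reported drug-related grade 3 or higher rate.

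**Working it through.** The plan states no figure to reproduce here; the question is what the rule does when applied.

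**Inputs.** The repeat rule and the once-per-patient count (Section 13.8); the endpoint (Section 13.3); a yes/no relationship (Section 9.3.3); CTCAE grades 1 to 5 (Section 9.3.2); 12 patients, or at most 15 (Sections 3.0 and 13.5).

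**Two ways to reduce the episodes of one term in one patient.**
- Separate maxima: the highest grade over all episodes, counted as related if any episode is related.
- Linked: the highest grade among the related episodes only.

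| Episode 1 | Episode 2 | Separate maxima | Linked |
|---|---|---|---|
| Anemia, grade 2, related | Anemia, grade 3, unrelated bleed | Related, grade 3 | Related, grade 2 |
| Grade 1, related | Grade 3, unrelated | Related, grade 3 | Related, grade 1 |
| Grade 1, related | Grade 3, related | Related, grade 3 | Related, grade 3 |
| Grade 3, related | Grade 1, unrelated | Related, grade 3 | Related, grade 3 |

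**Direction.** Two episodes, each with 5 grades and 2 relationship values, give 10 × 10 = 100 ordered combinations. The rules differ only when exactly one episode is related and the unrelated one has the higher grade. There are 10 grade pairs with one grade above the other, and the related episode may come first or second, so 2 × 10 = 20 combinations differ. Separate maxima are higher in all 20 and never lower; the other 80 agree.

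The grade 3 or higher count changes only if the related episode is grade 1 or 2 and the unrelated one grade 3, 4 or 5: 2 × 3 × 2 = 12 of the 20. These are logical counts, not probabilities; a few of the combinations, such as a first episode of grade 5, cannot occur in practice.

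**Size per patient.** One such patient adds 1/12 = 8.3 points, or 1/15 = 6.7 points, to that term's drug-related grade 3 or higher rate. A rate over all terms rises only if the patient has no other related grade 3 or higher event.

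**Size for the trial.** The documents give no frequency of such repeats. With an assumed share d of patients, the expected number of misclassified patients is N × d:

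| Assumed d | N = 12 | N = 15 |
|---|---|---|
| 0% | 0 | 0 |
| 2% | 0.24 | 0.30 |
| 5% | 0.60 | 0.75 |
| 10% | 1.2 | 1.5 |

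**What does not depend on the rule.** The decision on a larger study rests on 2 or more PSA50 responses in 12 patients (Section 13.5). The stopping rule counts grade 3-4 events that fail to resolve after four weeks off drug (Section 13.6). Neither uses the Section 13.8 summary.

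**The case against.** The strongest reply is that the sentence need not feed a joint table. Analyses of grade and causality may mean a worst-grade summary and a separate relationship summary, and for those the rule is right. The only grade table that Section 13.8 names does not mention relationship, and neither does the endpoint wording in Section 3.0. This stands as a fair reading, and it is why the point is conditional. It does not remove the gap: on that reading, the endpoint as Section 13.3 defines it has no repeat rule at all, and the same added sentence is needed.

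The protocol also narrows the cases. An event that worsens during its course is one event at its highest grade (Section 9.3.2), so only separate occurrences matter. Expected progression is generally not recorded as an adverse event (Sections 9.1.1 and 9.1.4), which weakens examples such as fatigue from progression; the anemia example does not rely on it. Calling an episode unrelated requires that its time course rule out a causal link (Section 9.3.3), a demanding test under continuous olaparib. All this stands, and it limits how often the problem can arise.

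Finally, the rule errs toward reporting more toxicity, the listing keeps each episode visible, and no decision threshold is set on a drug-related grade 3 or higher rate. That limits the severity. A listing still does not correct a summary rate, and a worst-grade table of all events gives the cautious view without assigning a causality that no episode supports.

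**Conclusion.** The gap is real and minor. If the Section 13.8 rule is applied to the Section 13.3 endpoint, the drug-related grade 3 or higher rate can be overstated and cannot be understated. The effect is 8.3 points (12 patients) or 6.7 points (15 patients) on a term's rate for each patient with a related episode below grade 3, a separate unrelated episode of the same term at grade 3 or higher, and no related episode of that term at grade 3 or higher. The total is unknown and may be zero.

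A reader might infer that the endpoint is overstated as a matter of course, by a factor that can be estimated. The documents do not support this. Suppose the fatigue figures in Table 1 (Section 4.2.6) are used, 6.4/59.1 = 0.108, as the chance that any one episode is grade 3 or higher, with two or three episodes, each related with probability 0.3 to 0.7, all independent. Separate maxima then overstate the rate 1.28 to 2.03 fold. But 0.108 is a ratio per patient, not per episode. With two episodes, the model puts 1 − (1 − 0.108)² = 20.4% of these patients at grade 3 or higher, about twice the source figure. The relationship probabilities and the independence have no source in the documents, and the factor applies only to patients with repeats of one term, whose number is unknown. It is not an estimate for this trial.

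**What to change.** In Section 13.8, limit the present repeat rule to separate summaries of grade and of relationship, and add:

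*For tables of drug-related adverse events by grade, restrict to episodes assessed as related and count each subject once per preferred term at the highest grade among those episodes. For tables of all adverse events, count at the highest grade regardless of relationship.*

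The cost is one sentence and a small change in the table program, best made before the tables are produced. Grade and relationship are already assessed for each event, so no new data are needed. The drawback is a slightly less conservative drug-related grade 3 or higher figure; the table of all events keeps the conservative view.

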#### 5.0 PATIENT SELECTION

# 5.1 Inclusion Criteria

Patients are eligible to be included in the study only if they meet *all* of the following criteria:

- [1] Have metastatic castration-resistant prostate cancer (prostate cancer progressing by PSA (rise by 25% on prior therapy) or imaging despite castrate levels of testosterone [<50 ng/dL] using standard measures of progression defined by Prostate Cancer Working Group).
- [2] Have a minimum PSA of 1 ng/mL.
- [3] Have a pathological diagnosis of prostate carcinoma.
- [4] Have been receiving and will continue to receive continuous hormonal ablation with surgical or medical castration with baseline testosterone <50ng/dL.
- [5] May be receiving bone-targeted agents.
- [6] May have received multiple lines of therapy including radium 223, sipuleucel T, and up to 2 lines of chemotherapy (One of 2 lines may be for hormone sensitive metastatic prostate cancer or both can be for castration resistant).
- [7] Age  $\geq$  18.
- [8] Have ECOG performance status 0-1 (Appendix A).
- [9] Be able to take oral medication and willing to consider a port for ease of administration of ascorbate.
- [10] Must have progressed on one systemic line of treatment (can include LHRH agonist/antagonist or orchiectomy and at least one additional line of therapy (abiraterone, enzalutamide, apalutamide, darolutamide, docetaxel, etc)).
- [11] Have normal organ and marrow function measured within 28 days prior to administration of study treatment as defined below:

- Absolute neutrophil count  $>1.5 \times 10^9/L$ -Platelets  $> 100,000/mm^3$ 

-Hemoglobin > 9g/dL with no blood transfusion in the

past 28 days

-Total bilirubin < 1.5 x ULN

-AST (SGOT)/ALT(SGPT)  $\leq$  2.5 x ULN (<5x ULN if with known liver

metastases provided bilirubin is normal

-Creatinine  $\leq$  1.6 x ULN (for patients with  $\geq$  1.6 x ULN, calculated

or measured creatinine clearance must be > 60

mL/minute (Cockcroft-Gault).

- [12] Men of reproductive potential and those who are surgically sterilized (i.e. post-vasectomy) must agree to practice effective barrier contraception that has an expected failure rate of <1% during and for 6 months after discontinuation of study treatment. Female partners should also use a highly effective form of contraception ([see **Appendix C** for acceptable methods]) if they are of childbearing potential.

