# Management of anemia

Table 7 Management of anemia

Hemoglobin	Action to be taken	
Hb < 10 but ≥ 8 g/dl (CTCAE Grade 2)	Give appropriate supportive treatment and investigate causality. Investigator judgement to continue olaparib with supportive treatment (eg transfusion) $or$ interrupt dose for a maximum of 2 weeks. If repeat Hb < 10 $but \ge 8$ g/dl, dose interrupt (for max of 2 weeks) until Hb $\ge 10$ g/dl and upon recovery dose reduction to 250 mg twice daily as a first step and to 200 mg twice daily as a second step may be considered.	
Hb < 8 g/dl (CTCAE Grade 3)	Give appropriate supportive treatment (e.g. transfusion) and investigate causality.  Interrupt olaparib for a maximum of 2 weeks until improved to Hb ≥ 10 g/dl.  Upon recovery dose reduce to dose should be reduced to 200 mg twice daily as first step. If the reduced dose of 200 mg twice daily is not tolerable, no further dose reduction is allowed and study treatment must be discontinued.	

Common treatable causes of anemia (e.g. iron, vitamin B12, or folate deficiencies and hypothyroidism) should be investigated and appropriately managed. In some cases management of anemia may require blood transfusions.

Management of neutropenia, leukopenia and thrombocytopenia

Table 8 Management of neutropenia, leukopenia and thrombocytopenia

Toxicity	Study treatment dose adjustment
CTCAE Grade 1-2	Investigator judgement to continue treatment or if dose interruption, this should be for a maximum of 2 weeks; appropriate supportive treatment and causality investigation
CTCAE Grade 3-4	Dose interruption until recovered to CTCAE grade 1 or better for a maximum of 2 weeks. If repeat CTCAE grade 3-4 occurrence, dose reduce olaparib to 250 mg twice daily as a first step and 200 mg twice daily as a second step
	Discontinue therapy in cases of febrile neutropenia and thrombocytopenia associated with hemorrhage

Adverse event of neutropenia and leukopenia should be managed as deemed appropriate by the investigator with close follow up and interruption of study drug if CTCAE grade 3 or worse neutropenia occurs.

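### Section 13.8's laboratory summaries cannot flag worsening from an abnormal baseline and name no worst on-treatment value, although the graded adverse-event tables still catch severe cases

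*Combined protocol and SAP*

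**What the plan says.** Laboratory measurements are part of the safety endpoint. Section 13.3 begins "Safety and tolerability will be defined by frequency of the drug-related adverse events by grade" and adds laboratory measurements and vital signs. Section 13.8 then gives two separate laboratory summaries:

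- a change summary: "Changes in vital signs, hematology and clinical chemistry parameters from baseline to the end of the study will be examined";
- a shift summary: "Treatment-emergent changes from normal to abnormal values in key laboratory parameters will be identified".

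Neither names a nadir, a peak or a change of grade. The terms normal and key are not defined.

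The same paragraph of 13.8 also has graded adverse-event summaries: "Toxicity will be tabulated by type and grade", under CTCAE v5.0, and "if the same AE occurs on multiple occasions, the highest grade and strongest relationship to study drug will be assumed".

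Two other sections bear on how the laboratory sentences would work. Section 5.1 [11] heads its entry limits "Have normal organ and marrow function measured within 28 days prior to administration of study treatment as defined below" and includes "Hemoglobin > 9g/dL with no blood transfusion in the" past 28 days. It also admits AST/ALT up to 2.5 x ULN (below 5 x with liver metastases), bilirubin below 1.5 x ULN, and creatinine up to 1.6 x ULN, or higher with a clearance condition. Table 7 grades hemoglobin from 8 to below 10 g/dL as Grade 2. For hemoglobin below 8 g/dL it requires supportive treatment and "Interrupt olaparib for a maximum of 2 weeks until improved to Hb ≥ 10 g/dl".

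**The concern.** A shift defined as normal to abnormal can happen only in someone who starts normal. Eligibility lets men in with values outside usual reference limits, and these men may have the least reserve. However far such a value worsens, the shift summary has no category for it.

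The change summary looks at one later point, the end of study. Toxicity that was managed and has recovered by then appears there only in reduced form, or not at all.

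Safety of the combination is the first secondary objective, and Section 4.2.8 says the two agents have not been combined before in this disease. Laboratory summaries are also the one part of the safety endpoint that needs no attribution. Section 13.3 counts drug-related events, and Section 9.3.3 allows the label related only when no other cause can be identified. A laboratory summary that works properly therefore adds information that the adverse-event count may not contain.

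**Working it through.** The plan states no figure for this point, so there is nothing to reproduce. The check applies the rules to example patients, then asks whether the size of the gap can be derived.

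**Step 1. Four illustrative courses.** The values are invented; the limits are the protocol's, except a lower limit of normal for hemoglobin of 13.0 g/dL, which is assumed.

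| Course | Shift flag, usual reference limits | Shift flag, Section 5.1 limits as normal | End-of-study change | Adverse-event tables |
|---|---|---|---|---|
| A. Hb 9.6, then 7.4, then 10.1 g/dL | No | Yes | 10.1 - 9.6 = +0.5 | Yes, Grade 3 (Table 7 action) |
| B. Hb 13.2 to 12.9 g/dL | Yes | No | -0.3 | Only if 9.3.1 is met |
| C. ALT 2.0, then 4.5, then 2.0 x ULN, no liver metastases | No | Yes | 0 | Yes if olaparib is held (8.1, drug-related, from 2.5 x ULN); Appendix D review from 3 x ULN |
| D. Creatinine 1.1, then 1.5, then 1.1 x ULN | No | No | 0 | Only if symptomatic, further tested or treated, dosing changed, or judged significant |

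A, B and C are classified in opposite ways under the two meanings of normal, so two analysts could report different results from the same data. D is flagged by neither reading. It stays below the 1.6 x ULN level in Section 8.1; I assume clearance stays at or above 51 mL/min, so that the retesting in 8.2.2.2 is not triggered. The rise is 0.4 x ULN, or 0.4/1.1 = 36% of baseline. Sections 7.9.1 and 7.9.2 list nephropathy and renal failure for ascorbic acid and raised creatinine for olaparib.

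**Step 2. Are severe hemoglobin falls lost?** No. Below 8 g/dL, Table 7 requires treatment and interruption. Section 9.3.1 makes an abnormal test an adverse event if it needs intervention or changes dosing. Section 9.1.1 includes deterioration of a pre-existing condition, 9.3.2 records the highest grade, and 13.8 tabulates it. By rule, the share of measured values below 8 g/dL missing from those tables is 0. Table 7 also calls for supportive treatment and investigation between 8 and 10 g/dL, so the unrecorded hemoglobin residue lies mainly at 10 g/dL and above.

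**Step 3. Is severe anemia likely here?** At the 20% grade 3-4 rate cited in Section 4.2.6, the expected number is 12 x 0.20 = 2.4, and the chance of at least one is 1 - 0.80^12 = 0.93. For 15 men these are 3.0 and 0.96. At the 17.4% in Table 1, the figures for 12 men are 2.1 and 0.90. Step 2 shows where these events are reported.

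**Step 4. Can the share missed by the shift sentence be derived?** Let q be the share of falls below 8 g/dL in men whose baseline is already abnormal. If any post-baseline value counts, the share missed by that sentence alone is q. The documents give neither a baseline distribution nor a lower limit of normal, so q must be assumed. Take baseline as normal with SD 1.5, truncated above 9 g/dL, and an independent fall with SD 1.5, set so that 20% go below 8 g/dL:

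| Assumed baseline mean (g/dL) | Assumed lower limit (g/dL) | q |
|---|---|---|
| 12.0 to 13.0 | 13.0 to 13.5 | 90% to 99% |
| 14.0 | 13.0 | 66% |
| 14.0 | 12.0 | 32% |

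The answer moves from a third to nearly all with the assumptions. It also concerns only events that Step 2 shows are reported elsewhere. For course D the documents support no figure.

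**Step 5. What does the end-of-study value hide?** A man who goes from 12 to below 8 and recovers to 10 g/dL shows 10 - 12 = -2, against a true fall of more than 4. This is understated but not erased. In the same model, 76%, 85% and 92% of men reaching below 8 g/dL (means 12.0, 12.5, 13.0) start above 10, so recovery to exactly 10 still leaves a net fall. Course A is the less typical case.

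**The case against.** The strongest reply is that the two laboratory sentences are not the safety analysis. The same paragraph of 13.8 lists adverse events individually and tabulates toxicity by grade with the worst grade kept. Every example that a clinician would call serious lands there. Section 5.1 offers a meaning of normal under which courses A and C are flagged. The change sentence could be read as covering the whole period from baseline to end of study. With 12 to 15 men, individual laboratory values can be listed.

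Most of this stands. A reader might infer that most severe hemoglobin drops would be scored as no treatment-emergent change. The documents do not support that. The shift sentence is one summary among several, it is not tied to the end-of-study value, severe drops are reported as graded adverse events, and the word most depends wholly on assumed baseline values. Nor does the end-of-study comparison miss everyone who has recovered to 10 g/dL.

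Three things remain:

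- The Section 5.1 meaning is an eligibility label, 13.8 does not adopt it, and Table 7 grades part of that range as Grade 2.
- The generous reading of the change sentence still specifies no worst value.
- Asymptomatic worsening that meets no criterion in 9.3.1 has no other place in the planned summaries, and these two sentences do not reliably show it.

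**Conclusion.** The point holds as a defect in the laboratory component of the safety endpoint. As written, the shift summary depends on an undefined word. Read against usual reference limits, it cannot flag worsening in men who enter abnormal, and the change summary can understate a transient nadir or peak.

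The effect is limited. The primary endpoint, the adverse-event-by-grade part of 13.3 and the stopping rule in 13.6 are untouched, and measured hemoglobin below 8 g/dL is captured at its highest grade. What is at risk is chiefly sub-threshold, asymptomatic worsening from an abnormal baseline, as in course D.

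No share of events missed can be derived from the documents; the 32% to 99% range in Step 4 rests on assumed inputs and describes the shift sentence alone. The conclusion assumes that normal means laboratory reference limits and that sites apply 9.3.1 as written. It is worth correcting before analysis, because the correction is cheap and the present wording permits opposite classifications of the same patient.

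**What to change.** In 13.8, replace the shift sentence with: *A treatment-emergent laboratory abnormality is any post-baseline value at least one CTCAE v5.0 grade worse than the last value before C1D1 dosing, whatever the baseline grade.* Then:

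- name the key parameters: hemoglobin, ANC, platelets, creatinine, ALT/AST and bilirubin;
- present, for each, a shift table of baseline grade against worst post-baseline grade, including unscheduled values;
- summarise change from baseline to the worst on-treatment value (lowest counts, highest chemistry values) alongside the end-of-study value, flagging hemoglobin measured after transfusion.

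Both additions are needed. A grade table shows worsening only when a grade boundary is crossed; the worst-value summary shows it in any case, course D included.

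One limit remains. Chemistry is scheduled weekly, but hematology is scheduled only on Day 1 of each cycle unless clinically indicated, so a reported nadir is the lowest measured value.

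The cost is a paragraph of text and a few more tables from data already collected. More laboratory worsening will be reported, and no patient's management changes.
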